6.3. Durability of Treatment Effect

The durability of treatment effect will be accessed based on the longitudinal responses of cellulites assessments of CR-PCSS and PR-PCSS. The number and percentage of responders at each level (ie, 1 level or 2 levels improvements) for CR-PCSS, PR-PCSS and their combinations (ie, composite score, 1 level or 2 levels improvements for both scores) associated with treated quadrants will be summarized by study day. The treatment failure is defined as active responders whose CR-PCSS and PR-PCSS return to the baseline or worse in an EN3835-treated quadrant during a certain follow-up period. The number and percentage will be summarized by study day, ie, Day 180, Day 360, Day 540, and Day 720.

Since there are 2 groups of responders, one group was subjects who were treated with EN3835 in the double-blind EN3835-201 study and followed up in the current EN3835-202 study up to 2 years. The durability analysis described above for this group will be based on the durability population in double-blind treated subjects. The other group will be subjects who will be treated with EN3835 and then followed up to 1 year in the current EN3835-202 study. The durability analysis for this group will be based on the durability population in open-label treated subjects.

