17.5.2. Secondary Efficacy Analysis

Secondary endpoints for treated quadrants include:

- Proportion of composite responders defined as subjects with an improvement in severity from baseline of at least 1 level of severity in the CR-PCSS and an improvement of severity from baseline of at least 1 level of severity in the PR-PCSS. (Day 71)
- Proportion at each level of improvement in the PR-PCSS (Day 71):
 - Proportion of patient responders defined as subjects with an improvement in severity from baseline of at least 2 levels of severity in the PR-PCSS
 - Proportion of patient responders defined as subjects with an improvement in severity from baseline of at least 1 level of severity in the PR-PCSS
- Proportion at each level of improvement in the CR-PCSS (Day 71):
 - Proportion of Investigator responders defined as subjects with an improvement in severity from baseline of at least 2 levels of severity in the CR-PCSS (Investigator rated)
 - Proportion of Investigator responders defined as subjects with an improvement in severity from baseline of at least 1 level of severity in the CR-PCSS (Investigator rated)

- Proportion of responders at each level of the I-GAIS (Day 71):
 - Proportion of Investigator global responders defined as subjects with a response of 1 (improved) or better in the Investigator GAIS assessment
- Proportion of responders at each level of the S-GAIS (Day 71):
 - Proportion of subject global responders defined as subjects with a response of 1 (improved) or better in the subject GAIS assessment
- Proportion of responders at each level of the subject satisfaction with cellulite treatment (Day 71)
- Change in the Hexsel CSS total score from screening visit to Day 71
- All secondary endpoints, except the Hexsel CSS total score, will be summarized by treated region (buttock or thigh) and overall using percentages. Change in Hexsel CSS total score will be summarized by treated region (buttock or thigh) and overall with descriptive statistics for continuous variables.

Observational endpoints include:

- Proportion of 2-point composite responders as defined by responses in the quadrant treated in study EN3835-201 who either maintained response, lost response but did not return to the baseline of study EN3835-201, or returned to the baseline of study EN3835-201.

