2. ANALYSIS POPULATIONS AND PHASES

The following populations will be considered in the statistical analysis of the study:

- Observation Population: The Observation population includes all subjects rolled over from study EN3835-201. The cellulite assessment evaluations and safety analyses on data collected during observation phase will be performed using this population.
- Safety Population: The Safety population will include all subjects who receive at least 1 dose of EN3835 in the current study. All safety analyses for the treatment phase will be performed using this population. For by region summaries, safety population is considered within each treatment course.
- Effectiveness Population: The Effectiveness population includes all safety subjects who have a baseline and at least 1 post-baseline assessment on both the CR-PCSS and PR-PCSS on the quadrant selected for treatment in the current study. All analysis of effectiveness for the treatment phase will be based on this population. For by region summaries, effectiveness population is considered within each treatment course.
- Durability Population: This population is defined as all active responders who have both CR-PCSS and PR-PCSS at 180 days or above. The active responders are subjects treated with EN3835 with improvements of at least 1 level on each

scale (CR-PCSS and PR-PCSS) at Day 71 visit compared to the baseline. Analysis of durability of treatment effect will be performed using this population.

- Durability Population for Double-blind Treated Subjects: This population is defined as all subjects in the durability population who showed an improvement of at least 1 level on each scale (CR-PCSS and PR-PCSS) at Day 71 visit compared to the baseline for the quadrant treated with EN3835 in double-blind study EN3835-201.
- Durability Population for Open-label Treated Subjects: This population is defined as all subjects in the durability population who showed an improvement of at least 1 level on each scale (CR-PCSS and PR-PCSS) at Day 71 visit compared to the baseline for the quadrant treated with EN3835 in the open-label study EN3835-202 study, who did not have the same quadrant treated with EN3835 in double-blind study EN3835-201. For by region summaries, this population is considered within each treatment course.

The following 2 phases will be summarized in the statistical analysis of the study:

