3. STATISTICAL METHODS AND CONSIDERATIONS

3.1. Descriptive Statistics

All analysis results will be presented in summary table using appropriate descriptive statistics, unless otherwise stated. The statistics include the number (count) and percentage for all categorical variables. The denominator will be based on the number of subjects in each column group in the summary table, unless otherwise stated. All continuous variables will be summarized with observed count, mean, standard deviation, median, minimum, and maximum value.

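### SAP 6.3 takes the 2-level durability percentages over all 1-level composite responders, so they do not show how well a 2-level response was maintained

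*Combined protocol and SAP*

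**What the plan says.** **Analysis set.** SAP section 2 says of the durability population: "This population is defined as all active responders who have both CR-PCSS and PR-PCSS at 180 days or above". On entry, it says: "The active responders are subjects treated with EN3835 with improvements of at least 1 level on each" of the two scales at Day 71. The double-blind and open-label subsets repeat that criterion: "This population is defined as all subjects in the durability population who showed an improvement of at least 1 level on each scale". No subset is defined by a 2-level response or by response on one scale.

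**Summaries.** SAP 6.3 tabulates "The number and percentage of responders at each level (ie, 1 level or 2 levels improvements) for CR-PCSS, PR-PCSS and their combinations" by study day. For the double-blind group, "The durability analysis described above for this group will be based on the durability population in double-blind treated subjects"; for the open-label group, "The durability analysis for this group will be based on the durability population in open-label treated subjects".

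**Denominator.** SAP 3.1 gives the general rule: "The denominator will be based on the number of subjects in each column group in the summary table, unless otherwise stated". SAP 6.3 states no other.

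**Loss of response.** The only loss measure in SAP 6.3 is treatment failure: an active responder whose CR-PCSS and PR-PCSS are back at baseline or worse. It is not specific to a response level.

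**Protocol Amendment 2, section 17.5.2.** The observational endpoints begin with "Proportion of 2-point composite responders as defined by responses in the quadrant treated in study EN3835-201 who either maintained response", then add those who lost response without reaching baseline and those who returned to it. The same three-way split is listed for 1-point composite responders and for 2- and 1-point responders on each scale. It is repeated for quadrants treated in the extension study.

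**The concern.** Durability is a secondary objective (SAP 1.3.2), and the 2-level composite at Day 71 is the primary cellulite endpoint in protocol Amendment 2, section 17.5.1. The natural question is how many of those who reached 2 levels still had it at Day 180, 360, 540 or 720. A table with all 1-level composite responders underneath does not answer it. A low 2-level figure could mean that the effect wore off, or that few subjects were at 2 levels to begin with. A reader of a section headed durability is likely to assume the first.

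The population also requires response on both scales. A subject who responded on CR-PCSS alone, or on PR-PCSS alone, is therefore missing from the single-scale durability results, although the single-scale endpoints in Amendment 2 are defined by response on that scale.

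**Working it through.** The plan states no durability figure, so there is nothing to reproduce. The check is denominator algebra.

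**Inputs**
- Denominator: all subjects in the durability subset (SAP 2, 3.1 and 6.3).
- s: share of that subset at the given level at Day 71. Not in the documents for 2 levels; assumed 0.2 to 0.8.
- r: share of those starters still at the level on the later day. Not given; assumed 0.5 to 1.0.
- g: share of the others who reach the level later. Not given; assumed 0 to 0.1.
- Every subject is taken to have a value on the later day.

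**Formulas**
- Percentage under SAP 6.3: P = s × r + (1 − s) × g
- Maintenance of response: r

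**Same percentage, different retention (g = 0)**

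| s | r (maintenance) | P under SAP 6.3 |
|---|---|---|
| 0.4 | 1.0 | 0.4 × 1.0 = 40% |
| 0.5 | 0.8 | 0.5 × 0.8 = 40% |
| 0.8 | 0.5 | 0.8 × 0.5 = 40% |

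**Range.** The lowest P is 0.2 × 0.5 + 0.8 × 0 = 10%. The highest is 0.8 × 1.0 + 0.2 × 0.1 = 82%. Over the same grid, maintenance runs only from 50% to 100%.

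**Does P respond to retention at all?** Yes. With s = 0.4 and g = 0, P is 40%, 32% and 20% for r = 1.0, 0.8 and 0.5.

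**Can the reader divide by the Day 71 percentage?** P / s = r + g × (1 − s) / s, which equals r only when nobody gains late. With s = 0.2, r = 0.8 and g = 0.1, P = 0.16 + 0.08 = 0.24, and 0.24 / 0.2 = 1.20, which cannot be a retention rate.

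**1-level results.** Everyone in the population was at least 1 level better on both scales at Day 71. So s = 1 for the 1-level composite and for each scale at 1 level, and P = r. These percentages are retention within this population.

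**Middle category.**
- For the 1-level composite, take the population, subtract the current 1-level composite responders, and subtract the treatment failures (both scales at baseline or worse, reading the SAP's conjunction literally). The remainder is the group that lost response without returning to baseline.
- For 2 levels this fails. A subject who slips from 2 levels to 1 is not a failure and is counted together with subjects who were never above 1 level.

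**The case against.** **The 2-level figure does carry information on retention.** This stands. A reader might infer that it measures only how many started at 2 levels. The algebra does not support that, because P falls as r falls. The fault is mixing.

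**The 1-level single-scale figures are sound.** This also stands. A reader might infer that every single-scale percentage has the wrong denominator. At 1 level it does not; the gap is the exclusion of one-scale responders. Likewise, the protocol's middle category is not wholly lost, since it can be derived for the 1-level composite.

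**Other tables cover the ground.** SAP 6.2.3 reports 1- and 2-level responders on both scales and the composite by study day, and SAP 6.2.2 does so on each scale for open-label quadrants. One-scale responders are thus counted over time. But 6.2.3 uses all subjects who rolled over, by parent-study treatment group, and neither section conditions on Day 71 response, so neither gives maintenance. A Day 71 row in the 6.3 tables is not clearly ruled out, but would give retention only with no late gain.

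**The SAP may follow another protocol version.** A reader might infer an undisclosed departure, because SAP section 9 lists only the cohort and observation-population changes. The documents do not establish that. SAP section 9 describes protocol 17.2.1 differently from the Amendment 2 text. The SAP has visits at Days 450 to 720 and an objective beyond 12 months that Amendment 2 lacks. It plans no interim analysis where Amendment 2 plans two. The 17.5.2 text that governs this SAP may not be among the pages available. The denominator problem does not depend on it.

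**It matters less in a safety study.** The primary objective is safety, the cellulite results are descriptive and uncontrolled, and the SAP names no primary cellulite endpoint. That limits the weight of the point, but durability is still a stated objective that the planned table leaves unreadable at 2 levels.

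**Full single-scale denominators are not available throughout.** This stands after Day 360. SAP 1.1 and 1.2 reserve the later visits for subjects treated with EN3835 in the parent study who improved at least 1 level on both scales.

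**Conclusion.** The point holds for the 2-level results (composite, CR-PCSS and PR-PCSS). As written, SAP 6.3 divides by all subjects at least 1 level better on both scales at Day 71. The percentage therefore combines starting share, retention and late gain, and cannot be read as maintenance of a 2-level response. This conclusion follows from the SAP text alone. Its size depends on quantities the documents do not give: on the assumed ranges above, the planned figure can lie anywhere from 10% to 82%, and a single value of 40% is compatible with retention from 50% to 100%.

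For 1-level single-scale results the point is narrower: the percentages are valid within the durability population but say nothing about subjects who responded on one scale only. A failure to disclose in SAP section 9 is not shown.

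**What to change.** In SAP 6.3:

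1. For each 2-level definition (composite, CR-PCSS, PR-PCSS), add a table restricted to quadrants that met it at Day 71. At each study day classify them as maintained, lost but better than baseline, or returned to baseline, as in protocol Amendment 2, section 17.5.2. For the composite, state whether one or both scales must be back at baseline; the both-scale rule already used for treatment failure would keep the three categories exhaustive.
2. Through Day 360, do the same for single-scale responders whether or not they were composite responders.
3. Beyond Day 360, state that single-scale results cover only 1-level composite responders, because the visit schedule follows only them.
4. If the governing protocol version keeps the 17.5.2 endpoints, list any remaining departure in SAP section 9.

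The cost is SAP wording and one Day 71 flag per definition, on data already collected; no visits are added. The downside is smaller n in the 2-level tables: a share s of the durability population for quadrants in it, so one fifth if s = 0.2. Report the counts beside the percentages.

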11.1.2. Subject Exclusion Criteria for Observation

None

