11.2. Treatment

Inclusion and exclusion criteria presented in section 11.2 apply only to those subjects in the open-label study who choose treatment.

At the time that the study drug blind is broken in the double-blind study EN3835-201, qualified subjects enrolled in the open-label study are eligible for treatment. A subject may participate in the observational period of this open-label study regardless of scoring of quadrant; however to receive treatment in this study, a subject must have at least 1 qualifying quadrant.

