11.2.2. Subject Exclusion Criteria for Treatment

A subject will be **excluded from treatment** in the study (but not from the observation assessments) if she:

1. Has used any of the following for the treatment of EFP on the legs or buttock within the timelines identified below or intends to use any of the following at any time during the course of the study:
 - Liposuction on the side of the body selected for treatment during the 12-month period before injection of study drug
 - Injections (eg, mesotherapy); radiofrequency device treatments; laser treatment; or surgery (including subcision and/or powered subcision) within the selected treatment quadrant during the 12-month period before injection of study drug
 - Endermologie or similar treatments within the selected treatment quadrant during the 6-month period before injection of study drug
 - Massage therapy within the selected treatment quadrant during the 3-month period before injection of study drug
 - Creams (eg, Celluvera™, TriLastin®) to prevent or mitigate EFP within the selected treatment quadrant during the 2-week period before injection of study drug
2. Is presently nursing a baby or providing breast milk for a baby
3. Intends to become pregnant during the study
4. Has received an investigational drug or treatment within 30 days before injection of study drug
5. Has a known systemic allergy to collagenase or any other excipient of study drug
6. Is currently receiving or plans to receive anticoagulant or antiplatelet medication or has received anticoagulant or antiplatelet medication (except for ≤150 mg aspirin daily) within 7 days before injection of study drug
7. Has a known recent history of stroke, bleeding, or other medical condition, which in the investigator's opinion would make the subject unsuitable for enrollment in this phase of the study

8. Presence of any clinically relevant conditions, that in the opinion of the Investigator would interfere with completing the study including, but not limited to, visual problems, hearing problems, cognitive impairment or acute mental illness

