12.2.2. Prohibited Procedures

The treatments and procedures listed in exclusion criteria are prohibited during the study.

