At each treatment course, subjects will receive 3 treatment sessions (Day 1, Day 22, and Day 43) unless the chosen quadrant has no further treatable edematous fibrosclerotic panniculopathy (EFP) dimples and the Investigator rates the quadrant a score of 0 on the Clinician Reported Photounumeric Cellulite Severity Scale (CR-PCSS). The same dimples within a quadrant or different dimples within a quadrant may be treated at each session but injections must all be within the selected quadrant for all 3 sessions. Each treatment session will be separated by approximately 21 days. Day 71 visit (end of treatment/early termination [EOT/ET]) will be performed for each subject. After Day 71, the subjects will be observed every 3 months from their first exposure to EN3835 up to a maximum of 1 year in each treated quadrant (including

both open-label and double-blind treated quadrants, if different quadrants were treated across both studies). Durability beyond Day 360 will be assessed in subjects who received active treatment in EN3835-201 and showed a composite improvement of at least 1 level on both the CR-PCSS and the Patient Reported Photonic Cellulite Severity Scale (PR-PCSS). In these subjects, the original quadrant treated in EN3835-201 will be assessed until the end of the current study, in addition to any treated quadrants occurring in the current study. Assessments of durability beyond Day 360 may also include subjects who opted not to receive additional treatments in EN3835-202.

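### SAP 6.3 has no rule for CR-PCSS and PR-PCSS scores taken after another cellulite procedure in the quadrant followed for durability

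*Combined protocol and SAP*

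**What the plan says.** **Durability in the SAP.** SAP section 2 sets the main durability population: "This population is defined as all active responders who have both CR-PCSS and PR-PCSS at 180 days or above". SAP 6.3 reports responders by study day and defines the opposite outcome: "The treatment failure is defined as active responders whose CR-PCSS and PR-PCSS return to the baseline or worse in an EN3835-treated quadrant". Failures are tabulated for Days 180, 360, 540 and 720. Beyond Day 360, only the quadrant given active drug in EN3835-201 is assessed (SAP Table 4). On who takes part, SAP 1.1 adds: "Assessments of durability beyond Day 360 may also include subjects who opted not to receive additional treatments in EN3835-202". SAP section 2 closes the observation phase for a quadrant when that same quadrant first receives EN3835 in study EN3835-202. SAP 8.1 fills a missed visit with the next observed score.

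**Other cellulite treatments in the protocol.** Protocol 12.2.2 states: "The treatments and procedures listed in exclusion criteria are prohibited during the study". The list is exclusion criterion 1 in protocol 11.2.2: liposuction, injections, radiofrequency, laser, surgery, endermologie, massage and creams. It also catches a woman who "intends to use any of the following at any time during the course of the study". Most items are tied to one place, for example "surgery (including subcision and/or powered subcision) within the selected treatment quadrant during the 12-month period before injection of study drug". Liposuction is tied to the side of the body instead. On who is bound, protocol 11.2 says: "Inclusion and exclusion criteria presented in section 11.2 apply only to those subjects in the open-label study who choose treatment". Protocol 11.1.2, headed "Subject Exclusion Criteria for Observation", lists none.

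**The concern.** A durability percentage should describe what remains of the EN3835 effect. Women who are losing response are plausibly the ones most inclined to try something else. A procedure in the followed quadrant would therefore tend to come after relapse and, if it worked, to improve the very scores that define durability. Without a rule, that recovery is credited to EN3835.

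Durability to 12 months and beyond is a secondary objective (SAP 1.3.2). SAP 6.3 is confined to EN3835 responders, so the section itself has no group without EN3835 in which a late recovery would stand out. The error would favour the drug.

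**Working it through.** **1. The plan's own figure.** Protocol 17.1 takes 95% of 350: 350 × 0.95 = 332.5, rounded up to 333. This reproduces, but it has no bearing here. The documents give no relapse rate and no uptake of other procedures, so the check is a reading of the rules followed by an illustration.

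**2. Does any SAP rule stop a post-procedure score from counting?**

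| SAP section | What governs use of a score | Names another cellulite procedure? |
|---|---|---|
| 2, durability population | Response at Day 71 and both scores at Day 180 or later | No |
| 2, observation phase | Ends when EN3835 is given in the same quadrant | No |
| 6.3, failure | Both scales back at baseline severity or beyond | No |
| 8.1, missed visits | Next observed score carried back | No |
| 3.3, deviations | Team may exclude data before lock | Not in the text shown; the checklist is a separate document |

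The SAP therefore has a cut-off for more EN3835 in the quadrant, but none for a different procedure there.

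**3. What that does to one woman.** Suppose a responder relapses, misses Days 360 and 450, has laser treatment in the followed quadrant, and at Day 540 scores one level better than baseline on both scales. She is a 1-level composite responder at Day 540. SAP 8.1 gives Days 450 and 360 the same scores, so she is also a responder at Day 360. She is a failure at neither day. Because failure needs both scales at baseline or worse, one regained level on either scale is enough to avoid failure at that visit.

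**4. How far does the ban reach?**
- *Quadrants treated open-label:* the ban clearly applies. Only the analysis rule is missing.
- *Observation-only women:* protocol 12.2.2 names no group, but the list it points to sits in criteria that bind only women choosing treatment. Observation has no exclusion criteria.
- *EN3835-201 quadrant of a re-dosed woman:* apart from liposuction, the listed items concern the quadrant selected for open-label treatment, which is a different one.
- *Beyond Day 360:* SAP Table 4 lists consent and inclusion/exclusion at Day 450. The criteria applied there are not in the text shown.

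**5. Illustration of size.** Let p be the true durable share, q the share of relapsers who have a procedure in the followed quadrant, and s the share of those scored as responders afterwards. All three are assumptions.

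Reported durable share = p + (1 − p) × q × s

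- p = 50%, s = 80%, q = 10%: 0.50 + 0.50 × 0.10 × 0.80 = 54%, or 4 points too high.
- Same p and s, with q = 5%, 20% and 30%: 52%, 58% and 62%.
- Smallest case tried (p = 70%, q = 5%, s = 50%): 0.30 × 0.05 × 0.50 = 0.75 points, about 1.
- Largest case tried (p = 30%, q = 30%, s = 100%): 0.70 × 0.30 × 1.00 = 21 points.

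**The case against.** The strongest reply is that the procedures are prohibited. Protocol 12.2.2 carries no exemption, whereas the section before it (12.2.1) expressly frees observation-only women from the medication restrictions. Sections 11.1.2 and 11.2 govern entry rather than conduct. On that reading the ban covers everyone, and a breach would be a deviation for SAP 3.3 to handle. A reader might infer from the exclusion criteria that women in follow-up are free to have these procedures without a deviation. The documents do not support that: the reach of the ban is ambiguous, and the Protocol Deviation Checklist and the Day 450 criteria are unseen. The protocol text shown is Amendment 2 or earlier, and it follows women only to 12 months.

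Other replies also have force:
- Failure in SAP 6.3 is assessed over a follow-up period. If it is cumulative, a relapse recorded before the procedure is not erased. The section does not say. Responder percentages by study day would be raised either way.
- Protocol 8.2 finds little evidence that the alternatives work, and relapsed women can elect EN3835 re-treatment instead. Both limit the effect. The same section does, however, describe an approved powered subcision device and a laser study reporting improvement for a year.
- SAP 6.2.3 summarises observation endpoints by EN3835-201 treatment group, so a placebo group does appear outside 6.3.
- Failure, censoring and use of all scores are each defensible in an uncontrolled, descriptive extension whose primary objective is safety. Counting one use of a cream as permanent failure would be harsh.

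None of this supplies the missing rule. Even a ban that covers everyone does not say how scores after a breach are analysed. Review under SAP 3.3 is case by case, and dropping a relapsed woman would itself remove a failure. The protocol's per-protocol population (17.2.5) does not appear in the SAP.

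**Conclusion.** The gap is real and worth closing. As written, SAP 6.3 and 8.1 use scores taken after another procedure in the followed quadrant as EN3835 response, unless the deviation review happens to remove them. The likely direction is towards overstated durability, assuming procedures mostly follow relapse and improve the scores.

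The size cannot be stated. The 1 to 21 point range rests wholly on assumed p, q and s and on failure not being cumulative. Two stronger inferences should be resisted:
- That the followed women are mostly those who took no open-label drug. SAP 1.1 says only that such women may be included, and no split is given.
- That a shift of 5 to 15 points is the expected size, for example a true 40% failure rate reported as 35% to 25%. That requires every user to have relapsed first, every one to regain a level, and no earlier failure to be retained. At the upper end, 15% of responders is 15/40 = 37.5% of all relapsers.

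**What to change.** **SAP 6.3.** Add a rule for recorded liposuction, injections, radiofrequency, laser, subcision or other surgery in the followed quadrant. From the date of the procedure, later CR-PCSS and PR-PCSS scores are not used as response, and the quadrant counts as a treatment failure at later study days.

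**SAP 8.1.** State that a score taken after such a procedure is not carried back to an earlier visit.

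**Sensitivity analyses.** Add one that censors at the procedure date. Handle endermologie, massage and creams in a sensitivity analysis only.

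**Protocol.** Reconcile 12.2.2 with 11.1.2 and 11.2, so that the women and quadrants the ban covers are clear.

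**Cost.** One extra derivation, some wording, and a slightly less favourable durability figure. Procedures are already collected at each visit (SAP Tables 2 and 4) with date, indication and description (protocol 12.2). The quadrant is not a named item there, so the description must identify it.
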